## 6. GENERAL STATISTICAL CONSIDERATIONS

### 6.1. General Principles

All continuous variables will be summarized using the following descriptive statistics: n (non-missing sample size), mean, SD, median, maximum and minimum. The frequency and percentages (based on the non-missing sample size) of observed levels will be reported for all categorical measures.

In general, all data will be listed, sorted by treatment, cohort, and participant, and when appropriate by visit number within participant. All summary tables will be structured with a column for each treatment in the order (3, 10, 30 mg/kg EV68-228-N, and Placebo) and will be annotated with the total population size relevant to that table/treatment, including any missing observations. In some safety tables, all participants who received active product (3, 10, 30 mg/kg EV68-228-N) will also be summarized together.

### 6.2. Timing of Analyses

The final analysis will be performed after the final data lock, and CSR completed when all primary safety endpoint data and all secondary immunogenicity and pharmacokinetics endpoint data are available and received by the SDCC.

### 6.3. Analysis Populations

#### 6.3.1. Modified Intent-to-Treat (mITT) Population

The mITT population includes all participants who received at least a partial dose of study product and contributed both pre- and at least one post-dose venous blood sample for immunogenicity testing for which valid results were reported. Descriptive summaries of immunogenicity data will be presented for the mITT population.

#### 6.3.2. Per-Protocol Population

In the final analysis, protocol deviations will be reviewed to determine which protocol deviations may affect the analysis.

The per protocol population includes all participants in the mITT subset with the following exclusions:

- Data from all available visits for participants found to be ineligible at baseline.
- Data from all visits subsequent to the protocol deviations that are considered to affect the science.
- Data from any visit that occurs substantially out of window.

#### 6.3.3. Safety Population

Safety Population is defined as any participant who received all or part of the study product. Summaries and analysis of safety data will be presented for the safety population.

#### 6.3.4. Pharmacokinetics Population

The PK population will consist of participants in the Safety Population who have at least one evaluable serum PK sample for the estimation of  $C_{max}$  or  $AUC_{0-\infty}$  and received a full dose. This set will be used to assess the

---

PK endpoints. Any participants or data values excluded from this analysis set will be identified, along with their reason for exclusion. Participants receiving placebo are excluded from PK analysis.

#### **6.4. Covariates and Subgroups**

The protocol does not define any formal subgroup analyses, and the study is not adequately powered to perform subgroup analyses.

#### **6.5. Missing Data**

All attempts will be made to collect all data per protocol. As missing data are expected to be minimal, no imputation will be performed for missing values. Any data point that appears to be erroneous or inexplicable based on clinical judgment will be investigated as a possible outlier.

#### **6.6. Interim Analyses and Data Monitoring**

Not applicable.

#### **6.7. Multicenter Studies**

Data will be pooled across all clinical sites. Center effects are not anticipated because the sites are using standardized procedures for infusion and assessment of solicited and unsolicited AEs, and the assessment of immunogenicity and PK endpoints will be performed at central laboratories.

#### **6.8. Multiple Comparisons/Multiplicity**

This is a Phase 1 study with multiple primary endpoints. Because analyses of primary endpoints are descriptive rather than hypothesis tests, no adjustments for multiple testing are planned.

## 7. STUDY PARTICIPANTS

### 7.1. Disposition of Participants

[Table 9](#) will present a summary of the reasons that participants were screened but not enrolled.

The composition of analysis populations, including reasons for participant exclusion, by Dose Cohort is presented in [Table 7](#). Individual participants who were excluded from analysis populations are presented in [Listing 5](#).

The disposition of participants in the study will be tabulated by Dose Cohort ([Table 6](#)). The table shows the total number of participants screened, enrolled, receiving treatment, completed final blood draws, terminated from study follow-up and the number completing the study.

A flowchart showing the disposition of study participants will be included ([Figure 1](#)). This figure will present the number of participants screened, enrolled, lost to follow-up, and analyzed, by treatment arm.

A listing of participants who terminated from study follow-up and the reason will be included in [Listing 2](#).

### 7.2. Protocol Deviations

A summary of participant-specific protocol deviations will be presented by the reason for the deviation, the deviation category, and Dose Cohort for all participants ([Table 4](#)). Deviations that are considered major deviations will be reviewed for possible exclusion from the Per-Protocol Population. All participant-specific protocol deviations and non-participant specific protocol deviations will be included in Appendix 3 as data listings ([Listing 3](#) and [Listing 4](#), respectively).

## **8. EFFICACY EVALUATION**

Not applicable.

## 9. SAFETY EVALUATION

### 9.1. Demographic and Other Baseline Characteristics

Summaries of age, sex, ethnicity, and race will be presented by Dose Cohort overall and by site ([Table 10](#), [Table 11](#), [Table 12](#), and [Table 13](#)). Ethnicity is categorized as Hispanic or Latino, or not Hispanic and not Latino. In accordance with NIH reporting policy, participants may self-designate as belonging to more than one race or may refuse to identify a race, the latter reflected in the CRF as “No” to each racial option.

Individual participant listings (Appendix 3) will be presented for all demographics ([Listing 6](#)).

#### 9.1.1. Prior and Concurrent Medical Conditions

All current illnesses and past pre-existing medical conditions will be MedDRA® coded using MedDRA dictionary version 27.1 or higher version.

Summaries of participants’ pre-existing medical conditions will be presented by MedDRA SOC, PT, and Dose Cohort ([Table 14](#)).

Individual participant listings will be presented for all medical conditions ([Listing 7](#)).

#### 9.1.2. Prior and Concomitant Medications

Summaries of medications that were started prior to dosing and continued at the time of dosing will be presented by WHO Drug Code Level 1, Level 2 and Dose Cohort ([Table 76](#)).

Individual participant listings will be presented for all prior concomitant medications ([Listing 17](#)).

### 9.2. Measurements of Treatment Compliance

Any participants who were enrolled but did not receive the infusion of study product will be presented by Dose Cohort as part of the participant disposition table ([Table 6](#)). A summarized list of dates of dosing by Dose Cohort and site is presented in [Table 8](#).

Date and time of study product administration, along with information on whether the participant was dosed according to protocol will be included in [Listing 8](#). A listing of infusion interruptions will be presented in [Listing 9](#).

### 9.3. Adverse Events

A treatment-emergent AE (TEAE) is defined as an AE that occurs during or after the study product infusion and up through the final visit. Only TEAEs will be documented as AEs in this study. When calculating the proportions of participants with AEs within a given MedDRA category, each participant will be counted once and any repetitions of AEs within a participant will be ignored, and the event will be reported according to the highest severity recorded (separately for related and unrelated AEs, when both severity and relatedness are tabulated). The denominators for percent values will be indicated within the table or table header.

An overall summary of AEs by Dose Cohort will be presented in [Table 23](#).

The number of AEs and number and proportion of participants reporting an AE or SAE that occurred in  $\geq 5\%$  of participants in any Dose Cohort will be presented by MedDRA SOC, and PT ([Table 24](#)).

### 9.3.1. **Solicited Events and Symptoms**

Solicited AEs will be collected from the end of the infusion through Day 3. Solicited AEs will be summarized by severity for each day post administration (Days 1-3) and as the maximum severity over all 3 days.

Additionally, solicited AEs will be analyzed using standard techniques, such as exact CIs, to summarize the proportion of participants reporting each symptom. Solicited AEs include headache, rash, nausea, vomiting, diarrhea, fatigue, and myalgia.

The proportion of participants reporting at least one solicited AE will be summarized for each solicited AE. The 95% CI calculated using Clopper-Pearson methodology from a binomial distribution (SAS Proc Freq with a binomial option) will be presented (Table 25).

- The maximum severity of solicited symptoms per participant by day will be presented graphically in Figure 3.
- The proportion of participants experiencing solicited events, Clopper-Pearson 95% CI, and difference of proportion from the placebo group will be summarized in Table 26.
- The number and percentage of participants experiencing solicited events by symptom, maximum severity, will be summarized in Table 27.
- The number and percentage of participants experiencing solicited events by symptom, maximum severity and day after infusion will be summarized in Table 28, Table 29, Table 30, and Table 31.
- Solicited AEs by participant will be presented in Listing 11.

### 9.3.2. **Unsolicited Adverse Events**

Unsolicited AEs will be collected from the time of infusion through Day 29. Unsolicited AEs will be coded by MedDRA for PT, HLT, and SOC. The proportion of participants reporting at least one unsolicited AE will be summarized by MedDRA SOC, HLT and PT post infusion. Denominators for percentages are the number of participants who received the infusion being summarized.

AEs by participant will be presented in Listing 12.

The following summaries for unsolicited AEs will be presented by MedDRA SOC, HLT, PT, and Dose Cohort:

- The incidence and total frequency of AEs with Pearson-clopper 95% CI (Table 32)
- Summary of maximum severity and relationship to study product (Table 33 and Table 34)
- Participant incidence and total frequency of related adverse events by Dose Cohort (Table 35)
- Participant listing of serious AEs (Table 36)
- Participant listing of non-serious AEs of moderate or severe grade (Table 37)
- Listing of other significant AEs (Table 38)
- Listing of Unanticipated Problems (UPs) (Table 39, Table 40)
- Bar chart of non-serious related AEs by severity and MedDRA SOC (Figure 4)
- Bar chart of non-serious related AEs by maximum severity and MedDRA SOC (Figure 5)

## 9.4. Deaths, Serious Adverse Events and other Significant Adverse Events

The following listings will be presented including Participant ID, Age (years), Adverse Event Description, Adverse Event Onset Date/End Date, Dose Received/Days Post Dose, Reason Reported as an SAE, Relationship to Treatment, Alternate Etiology if not Related, Outcome, and Duration of Event (days):

- Deaths and Serious Adverse Events ([Table 36](#))
- Non-serious unsolicited, moderate or severe AEs, which are grade 2 or more ([Table 37](#))

Other significant AEs, including NOCMCs, MAAEs, ([Table 38](#)) and UPs ([Table 39](#), [Table 40](#)).

## 9.5. Pregnancies

For any participants in the Safety Population who became pregnant during the study, every attempt will be made to follow these participants to completion of pregnancy to document the outcome, including information regarding any complications with pregnancy and/or delivery. Listings of pregnancies and outcomes will be presented ([Listing 19](#), [Listing 20](#), [Listing 21](#), [Listing 22](#), and [Listing 23](#)).

## 9.6. Clinical Laboratory Evaluations

Clinical evaluations will be done to evaluate safety endpoints. These evaluations will include monitoring and recording of AEs and SAEs, clinical safety laboratory test results, VS measurements, 12-lead ECG results, and physical examination findings. The timing and frequency of all safety assessments are listed in the SOA ([Table 2](#)).

Toxicity grading criteria for clinical laboratory results can be found in [Table 5](#). Unscheduled clinical laboratory evaluations will be included in listings but excluded from tabular and graphical summaries, except when calculating the maximum severity post-baseline. Any pre-existing abnormal lab results at Screening and Baseline will be graded and presented in listings. The following parameters will be presented (in order): Chemistry - Creatinine, Total Bilirubin, ALT; Hematology - Hemoglobin (Hgb), WBC, Platelets (PLT); Hypersensitivity testing. Hypersensitivity testing will be conducted if a participant experiences anaphylaxis or an anaphylactoid event related to the infusion. One sample will be obtained at approximately 15 minutes prior to the infusion; if the participant experiences a reaction, three additional samples will be drawn: 1) at the onset of symptoms, 2) 2 or more hours after onset of symptoms, and 3) after resolution of symptoms. The hypersensitivity panel will measure complement levels and activity (C3, C4, and CH50), Immunoglobulin E (IgE) levels, and tryptase on serum.

Participants with abnormal laboratory results, which are Grade 1 or higher, will be listed in [Table 41](#), [Table 42](#), and [Table 43](#) for chemistry, hematology, and hypersensitivity, respectively. A full listing with all laboratory results will be listed in [Listing 1](#) and [Listing 2](#) for chemistry and hematology, respectively.

### 9.6.1. Clinical Laboratory Evaluations – Chemistry

Summaries of the number of participants with chemistry laboratory results, by grade severity, will be presented in [Table 44](#), [Table 45](#), [Table 46](#), and [Table 47](#).

Summaries of the number of participants with abnormal chemistry laboratory results related to study treatment, by grade severity, will be presented in [Table 48](#), [Table 49](#), [Table 50](#), and [Table 51](#).

Descriptive statistics including mean, SD, median, minimum and maximum values by time point, and changes from baseline, for each laboratory parameter will be summarized in [Table 52](#), [Table 53](#), and [Table 54](#).

Changes in laboratory values will be presented in [Figure 6](#), [Figure 7](#), and [Figure 8](#) for Creatinine, Total Bilirubin, and ALT, respectively.

### 9.6.2. Clinical Laboratory Evaluations - Hematology

A summary of the number of participants with hematology laboratory results, by grade severity, will be presented in [Table 55](#), [Table 56](#), [Table 57](#), [Table 58](#) and [Table 59](#).

A summary of the number of participants with abnormal hematology laboratory results related to study treatment, by grade severity, will be presented in [Table 60](#), [Table 61](#), [Table 62](#), [Table 63](#), and [Table 64](#).

Descriptive statistics including mean, SD, median, minimum and maximum values by time point, and changes from baseline, for each hematology laboratory parameter, will be summarized in [Table 65](#), [Table 66](#), and [Table 67](#). Changes in laboratory values will be presented in [Figure 9](#), [Figure 10](#), and [Figure 11](#) for Hgb, WBC, and PLT, respectively.

## 9.7. Vital Signs and Physical Examinations

Toxicity grading criteria for VS results can be found in [Table 5](#). Vital signs will be obtained on Day 1, Day 2, Day 3, Day 8, Day 15, and Day 29 of the study. Unscheduled VS measurements will be listed, but excluded from tabular and graphical summaries by time point, except when calculating the maximum severity post baseline. Refer to Section [3.3.1](#) for the definition of baseline. If VS measurements are repeated, the following rules will be used to determine which VS measurement to use for analyses if repeat measurements occur:

1. If the first replicate is normal, then it will be used for analysis.
2. If the first and second replicates are both abnormal, then the replicate with the higher severity will be used for analysis.
3. If the first replicate is abnormal, the second replicate is normal, and the third replicate was not performed, then the first replicate will be used in the analysis.
4. If the first replicate is abnormal, the second replicate is normal, and the third replicate is normal, then the second replicate will be used in the analysis.
5. If the first replicate is abnormal, the second replicate is normal, and the third replicate is abnormal, then the abnormal replicate with the higher severity will be used for analysis.

VS parameters that have grading criteria for both decreases (result lower than normal range) and increases (result higher than normal range) will be summarized separately by direction.

VS results will be summarized in tables by parameter, Dose Cohort, and time point ([Table 68](#), [Table 69](#), [Table 70](#), [Table 71](#), [Table 72](#), [Table 73](#), and [Table 74](#)).

All individual VS measurements, including height, weight, and oximetry measurements (SpO2) will be presented in [Listing 15](#).

Focused physical examinations performed on Day 1, Day 3, and Day 8. Symptom-driven physical examinations performed on Day 15, Day 29, Day 61, Day 91 and Day 121 if indicated based on review of complete medical history and any updates obtained by interview of participants since the previous visit.

Abnormal physical exam findings will be presented in [Listing 16](#).

## **9.8. 12-Lead Standard Electrocardiogram**

Summary of 12-lead standard ECG change in overall interpretation from baseline will be shown by Dose Cohort and time point ([Table 75](#)).

A listing of ECG overall interpretations and comments will be presented in [Listing 24](#).

## **9.9. Prior and Concomitant Medications**

Prior and concomitant medications will be coded to the Anatomical Therapeutic Classification using the WHO Drug Dictionary. The use of prior and concomitant medications taken during the study will be recorded on the CRFs. A by-participant listing of concomitant medication use will be presented. The use of concomitant medications during the study will be summarized by WHO Drug Code Level 1, Level 2 and Dose Cohort ([Table 76](#)). Individual participant listings will be presented for all prior concomitant medications ([Listing 17](#)).

## **9.10. Other Safety Measures**

Not Applicable.

## 10. PHARMACOKINETICS

EV68-228-N concentrations and PK parameters will be summarized by Dose Cohort. Statistics include the arithmetic mean, median, SD, geometric mean (GM), coefficient of variation (CV), minimum, and maximum. CV will be calculated using the method for log-normally distributed data and reported as a percent:

$$CV\% = \sqrt{\exp(s^2) - 1} \times 100\%, \text{ where } s^2 \text{ is the standard deviation of the log-transformed data}$$

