### 3.3.4. Pharmacokinetic Parameters

$AUC_{0-\infty}$  is defined as the AUC from the time of dosing extrapolated to time infinity based on the last observed concentration ( $C_{last}$ ) and the elimination rate constant ( $\lambda_z$ ), where  $C_{last}$  is defined as the last observed positive concentration above the lower limit of quantitation (LLOQ) and  $\lambda_z$  is defined as the first-order rate constant associated with the terminal (log-linear) portion of the curve describing the rate of elimination from serum. Estimated by linear regression of time vs. log concentration.  $AUC_{0-\infty}$  will be computed by adding  $AUC_{0-last}$  to an area extrapolated by  $C_{last}$  divided by  $\lambda_z$ , as shown below:

$$AUC_{0-\infty} = AUC_{0-last} + \frac{C_{last}}{\lambda_z}$$

$AUC_{0-last}$  is defined as the AUC from the time of dosing to the time of the last quantifiable concentration above the LLOQ based on observed concentrations.

$AUC_{0-48}$  is defined as the AUC from the time of dosing to the time of the last quantifiable concentration above the LLOQ up to and including the nominal 48 hr time point based on observed concentrations.

Maximum serum concentration ( $C_{max}$ ) is defined as the maximum observed concentration, occurring the time of maximal serum concentration ( $T_{max}$ ), in serum following the first dose of EV68-228-N.

$T_{max}$  is defined as the time at which the maximum observed serum concentration occurs. Because non-steady-state data is collected, the entire curve is considered. If the maximum observed concentration is not unique, then the first maximum is used.

---

The terminal elimination half-life ( $t_{1/2}$ ) is defined as the time it takes serum concentrations to reduce by 50% during the terminal elimination phase and will be estimated by the natural logarithm of 2 ( $\ln(2)$ ) divided by  $\lambda_z$ .

Total serum clearance (CL) is defined as the total clearance and represents a volume that is cleared of the molecule of interest per hour. It will be calculated as the dose divided by the  $AUC_{0-\infty}$ , as shown below:

$$CL = \frac{Dose}{AUC_{0-\infty}}$$

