## 4. INVESTIGATIONAL PLAN

### 4.1. Overall Study Design and Plan

This is a Phase 1, randomized, placebo-controlled, double-blinded study to assess the safety and PK of single IV administrations of EV68-228-N in healthy adult volunteers.

Three doses (3, 10 and 30 mg/kg) of EV68-228-N will be evaluated in three separate, sequential cohorts (N = 12, each cohort) in this single dose escalation study. The cohorts will be randomized in a 5:1 randomization scheme for EV68-228-N and placebo. The first two participants in each cohort will serve as sentinels. Sentinel participants may be located at different sites. Sentinel safety data will be collected through Day 3 before submitting to the Protocol Review Safety Team (PSRT) for review. The PSRT is comprised of the Principal Investigator (PI), the DMID Medical Monitor, and the DMID Medical Officer.

Data to be reviewed will include clinical data collected from Visits 1, 2 and 3, the results of laboratory testing conducted at these visits, solicited AEs and the passive reporting of AEs through Day 3. From the time of infusion of the sentinels to at least 48 hours after infusion, no new participants will be given study product or placebo, but screening may continue. If no safety signal is detected in the sentinel group, and after approval from the DMID Medical Monitor, the remaining 10 participants in the cohort will be dosed following the overall 5:1 randomization scheme.

All participants will be actively monitored for AEs and safety laboratory data following dosing through Day 8. Data will be reviewed by the PSRT and discussed with the SMC for their concurrence before advancing to the next cohort. Electronic review of the safety data by the SMC is required prior to the cohort dose escalation when halting rules are met or there are any safety concerns.

Assuming no safety concerns are identified after review of the first cohort safety data through Day 8, enrollment of Cohort 2 will begin. The dose of EV68-228-N will be increased to 10 mg/kg for the second cohort. The same sentinel design and safety plan will be used to evaluate sentinel participants in Cohort 2 and determine whether to enroll the remaining participants in Cohort 2. In addition, the same sentinel design and safety plan will be used for Cohort 3, which will evaluate the 30 mg/kg dose.

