## 5. SAMPLE SIZE CONSIDERATIONS

As a Phase 1, first-in-human study, the number of participants was chosen principally on feasibility and using a 5:1 randomization scheme. Thus, three cohorts of 10 participants each (n=30) and 6 placebo recipients (total N=36) are proposed. With 10 participants in each cohort receiving study product, the chance of observing at least one AE of probability 20% or more is approximately 89.3% (see [Table 3](#)). Therefore, if no AEs of a given type occur in an active dose group, we can be relatively confident that they will occur in fewer than 20% of people once the treatment is implemented.

PK parameters are not a primary outcome of the study, so it has not been powered for this, however with a sample size of 10 participants per dose level, assuming the pharmacokinetics are not dose proportional, a parameter with a coefficient of variation of 120% or less has a 90% chance to be observed within 80% and 120% of the geometric mean.

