### **13. REPORTING CONVENTIONS**

The mean, SD, and other statistics will be reported to 1 decimal place greater than the original data. The minimum and maximum will use the same number of decimal places as the original data. Proportions will be presented as 2 decimal places; values greater than zero but <0.01 will be presented as “<0.01”. Percentages will be reported to the nearest whole number; values greater than zero but < 1% will be presented as “<1”; values greater than 99% but less than 100% will be reported as >99%.

Drug concentrations, AUC values, Cmax and their summary statistics will have the same format as the drug concentrations reported by the bioanalytical laboratory. Other PK parameters will be reported to 1 decimal place.

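### The CV% formula in SAP Section 10 defines s² as the standard deviation instead of the variance, and CL in L/h at one decimal prints any value below 0.05 as 0.0

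*SAP*

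**What the plan says.** **CV%.** SAP Section 10 states the method: "CV will be calculated using the method for log-normally distributed data and reported as a percent". The formula that follows is CV% = √(exp(s²) − 1) × 100%, and s² is glossed as follows: it "is the standard deviation of the log-transformed data". The base of the logarithm is not named. The shells of Tables 78 and 80 carry a CV% row with no formula or footnote, and Section 15 records no changes.

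**Clearance.** Section 3.3.4 defines CL as dose over AUC to infinity and says it "represents a volume that is cleared of the molecule of interest per hour". Section 13 gives concentrations, AUC and Cmax the laboratory's format and then says: "Other PK parameters will be reported to 1 decimal place". Tables 79 and 80 head the CL column in L/h with the shell XXX.X. In Table 80 that format also covers the mean, SD, minimum, maximum and geometric mean.

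**Vz.** Section 3.3.4 defines Vz as a volume. Table 80 heads its column in L, Table 79 in h.

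**The concern.** If s is the SD on the natural-log scale, s² is the variance and the printed formula is the standard log-normal CV. The SAP's sentence assigns the SD to s² itself, which contradicts both the symbol and the named method. A programmer who follows the definition puts the SD in the exponent; one who follows the method puts the variance there. For modest CVs the two results differ about twofold.

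The CL point is one of display. An antibody sampled to Day 121 is presumably expected to clear slowly, and a slowly cleared drug can have a CL well under 0.1 L/h. At one decimal the CL columns could then show 0.0 for every participant and cohort. CL is a named secondary PK parameter, and Section 2.1 says the PK data will support the choice of a target dose for later trials.

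**Working it through.** The SAP gives no numerical CV result and no expected CL, so there is no figure of its own to reproduce. The check is of the formula and of the rounding.

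**1. CV%: variance against the literal definition**

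For log-normal data with log-scale SD σ, the true CV is c = √(exp(σ²) − 1), so σ = √ln(1 + c²). The literal SAP rule prints √(exp(σ) − 1). The true CVs below are illustrative, except 120%, which is the limit in Section 5 ("a parameter with a coefficient of variation of 120% or less").

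| True CV | σ = √ln(1 + c²) | Printed by the literal rule |
|---|---|---|
| 20% | 0.198 | 47% |
| 30% | 0.294 | 58% |
| 40% | 0.385 | 69% |
| 120% | 0.944 | 125% |
| 131% | 1.000 | 131% |
| 150% | 1.086 | 140% |
| 200% | 1.269 | 160% |

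Worked line for 30%: ln(1 + 0.09) = 0.0862; σ = √0.0862 = 0.294; √(exp(0.294) − 1) = 0.584.

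The readings cross where σ = σ², that is at σ = 1, where CV = √(e − 1) = 131.1%. Below this the literal rule overstates the CV; above it, it understates.

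As a check on which version is correct, 2,000,000 simulated log-normal draws at σ = 0.2, 0.3 and 0.5 gave CVs of 20.2%, 30.7% and 53.3%. The variance version gives the same three values; the literal version gives 47.1%, 59.1% and 80.5%.

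**2. CL at one decimal in L/h**

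Any value below 0.05 prints as 0.0: 0.003, 0.01, 0.02 and 0.0499 all do, and 0.05 prints as 0.1.

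In terms of exposure, CL = dose/AUC is below 0.05 L/h when AUC exceeds dose/0.05. At 3 mg/kg and an assumed 70 kg, the dose is 210 mg and the threshold is 210/0.05 = 4,200 mg·h/L, or 4.2 million ng·h/mL.

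Whether this happens depends on elimination, which the SAP does not quantify. From the Section 3.3.4 definitions, CL = ln 2 × Vz / t½. The Vz and half-life values below are assumptions.

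| Vz | Half-life | CL (L/h) | Prints as |
|---|---|---|---|
| 3 L | 28 days | 0.0031 | 0.0 |
| 5 L | 14 days | 0.0103 | 0.0 |
| 10 L | 7 days | 0.0413 | 0.0 |
| 10 L | 5 days | 0.0578 | 0.1 |
| 7 L | 3 days | 0.0674 | 0.1 |

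Worked line: 0.6931 × 10 / (24 × 7) = 0.0413. Over Vz 3–10 L and half-life 7–28 days, CL runs from 0.003 to 0.041 L/h and always prints as 0.0.

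Setting CL = 0.05 L/h gives the longest half-life that avoids a printed 0.0: t½ = ln 2 × Vz / (0.05 × 24) days, which is 1.7 days (3 L), 2.9 days (5 L), 4.0 days (7 L) and 5.8 days (10 L).

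**3. Can CL be recovered from the other columns?**

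Yes, as Vz × ln 2 / t½. Rounding Vz and t½ (in hours) to one decimal gives a relative error of at most about 0.05/Vz + 0.05/t½: 1.7% (3 L, 28 days), 1.0% (5 L, 14 days) and 0.5% (10 L, 7 days).

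**The case against.** The strongest reply is that the CV definition is a slip that corrects itself. The sentence names the log-normal method and uses the symbol s², and both point to the variance, so an experienced programmer would very likely use it. The distortion arises only if the gloss is followed against the method. CV% is also descriptive and feeds no test, and Tables 78 and 80 show the mean and SD beside it, so a CV of 47% next to a ratio near 20% could be noticed. This lowers the chance of harm, but the SAP still states the rule wrongly and nothing in it settles the matter.

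On CL, the SAP gives no elimination values, so the columns of 0.0 are conditional, and faster elimination avoids them. That is right. Section 13 also opens with a general rule ("The mean, SD, and other statistics will be reported to 1 decimal place greater than the original data"), which might give the summaries a second decimal. The Table 80 shell does not apply it to CL, and two decimals would still print 0.003 as 0.00. The N and CV% rows for CL stay informative in any case, and individual values can be recovered.

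The Vz heading is a plain typing error that should mislead nobody, since Table 80 and the definition agree. It is worth correcting in the same pass.

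**Conclusion.** The concern holds in all three parts.

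- **CV%:** the definition of s² is wrong as written. Followed literally, it gives 47% for a true 20% and 58% for a true 30%, agrees only at 131%, and understates above that. This rests on no assumption about the data beyond the log-normal method the SAP itself names. It matters only if the gloss is programmed.
- **CL:** that values below 0.05 L/h print as 0.0 is certain. That all values would do so rests on the assumed Vz of 3–10 L and half-life of 7–28 days. The defect is in display only: estimation, AUC, t½ and Vz are untouched.
- **Vz:** the unit in Table 79 is wrong.

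No primary endpoint is affected. These should be fixed because the CV definition governs a statistic used throughout the PK tables and the corrections cost almost nothing.

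**What to change.** 1. In Section 10, define s² as the variance of the natural-log-transformed data. This also settles the base of the logarithm.
2. In Section 13 and Tables 79 and 80, report CL in mL/h, which keeps the per-hour definition of Section 3.3.4 and turns the assumed range into 3.1–41.3 mL/h at one decimal. Alternatively, keep L/h and report CL to three significant figures. L/day at one decimal is not enough: 0.07–0.99 would print as 0.1–1.0.
3. In Table 79, change the Vz unit from h to L.

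The cost is one word replaced and the log base named in Section 10, one sentence in Section 13 and, with the mL/h option, three column headings (CL in both tables, Vz in Table 79), made before the tables are programmed. Neither the data nor the design changes.
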